6.1 DETERMINATION OF SAMPLE SIZE

The primary efficacy endpoint of this study is the proportion of patients who achieve CRR. Based on the NOBILITY trial, it is estimated that approximately 30% of patients with proliferative LN who are receiving MMF will achieve CRR at Week 76 and that the addition of obinutuzumab to MMF will induce an overall CRR rate of 50% at Week 76. On the basis of these assumptions, a total of 252 patients randomized to obinutuzumab and placebo groups in a 1:1 ratio (126 patients in each of the obinutuzumab and placebo- treated-groups) stratified by region and race will yield approximately 90% power to compare the combined obinutuzumab treatment group with the placebo group at the two-sided $\alpha = 0.05$ significance level using a Cochrane-Mantel-Haenszel (CMH) test, assuming the same CRR proportions across the strata. Patients randomized to obinutuzumab-treated group will be further randomized to obinutuzumab Arm 1 and obinutuzumab Arm 2 in a 1:1 ratio stratified by region and race.

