2.1 STATISTICAL HYPOTHESES

The primary efficacy analysis for this trial will compare obinutuzumab (combined treatment groups) with placebo on the basis of CRR at Week 76 to demonstrate superiority of obinutuzumab over placebo. The following null and alternative hypothesis will be tested at a two-sided 0.05 significance level:

H₀: P_{Obinutuzumb} = P_{Placebo} versus

H_a: P_{Obinutuzumb} ≠ P_{Placebo}

for which the P_{Obinutuzumb} and P_{Placebo} refer to proportion of patients who achieve CRR for obinutuzumab (combined treatment groups) and placebo respectively.

2.1.1 Multiplicity Adjustment

Secondary endpoints will be tested to compare obinutuzumab (combined treatment groups) with placebo groups for the superiority of obinutuzumab over placebo. To control the overall type I error, a fallback method maintaining a fixed sequence for testing will be used.

The sequence for endpoint testing will be the primary endpoint, followed by key secondary endpoints in the following order:

- Proportion of patients who achieve CRR with successful prednisone taper at Week 76
- 2. Proportion of patients who achieve a proteinuric response at Week 76
- 3. Change in eGFR from baseline to Week 76

If the primary endpoint test is significant at two-sided alpha level 0.05, the first key secondary endpoint in the sequence, CRR with successful prednisone taper, will be tested at alpha level 0.05.

If the CRR with successful prednisone taper is not significant, the testing stops and the endpoints after it in the sequence will be deemed non-significant.

If the CRR with successful prednisone taper is significant, the alpha 0.05 will be split as 0.04 and 0.01 to the next two endpoints, the proteinuric response and the change in eGFR, respectively.

If the proteinuric response endpoint is significant at 0.04 alpha level, this alpha is unused and will be passed to the change in eGFR endpoint giving a total alpha for the change in eGFR endpoint test of 0.05 (0.01+0.04). The change in eGFR endpoint test will then be performed at alpha level 0.05.

If the proteinuric response endpoint is not significant at level 0.04, the change in eGFR endpoint will be tested at the originally reserved alpha of 0.01.

[figure not shown]
If the change in eGFR is not significant at either 0.05 or 0.01 depending on whether the proteinuric response endpoint was significant, the testing stops.

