Early study withdrawals due to reasons other than lack of efficacy will be considered as having missing data.

The missing UPCR and eGFR values will be imputed by the multiple imputation model specified for the primary endpoint in Section 4.2.2 using data from the patients who did not experience death, treatment failure or early study withdrawal due to lack of efficacy.

The death or renal related event endpoint for patients who withdrew early from the study for reasons other than lack of efficacy will then be evaluated based on only the following criteria using the imputed UPCR and eGFR values:

- Worsening proteinuria, defined as a confirmed ≥50% increase in UPCR to a value ≥3
- Worsening eGFR, define as a confirmed ≥30% decrease in eGFR to a value <60

The death or treatment failure will not be imputed.

Worsening proteinuria will be assessed based on 24-hour UPCR which is collected at Week 24, 50 and 76 as per the protocol.

Imputation of eGFR will be made only for the Weeks 24, 36, 50, 64, and 76 as these visits are included in the imputation model (Section 4.2.2). If eGFR values worsened at other missing visits (Weeks 2, 4, 12, 26, and 52) that are not imputed, the worsening due to disease activity should be captured at the next observed or imputed visits. Study withdrawals who have not achieved the event following imputation of their UPCR or eGFR data will be assumed to have not had the event.

The multiple imputation parameters, analysis and pooling steps will be similar to the methods specified in the Section 4.2.2.

4.3.1.5 Mean Change in eGFR from Baseline to Week 76

Change in eGFR from baseline at Week 76 will be analyzed using Analysis of Covariance (ANCOVA) model. The response variable in the model will be change in eGFR from baseline at Week 76. Treatment group (combined obinutuzumab vs. placebo), baseline eGFR and the stratification factors race and region will be included in the model as independent variables. The adjusted difference between the treatment group with 95% CI and p-value will be presented.

The eGFR values for patients who died will be imputed with 0 (composite strategy). All other intercurrent events (specified in Section 4.3) will be handled using treatment policy strategy.

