Missing data will be imputed by multiple imputations using FCS predicted mean matching method. A set of candidate donors with 5 members is chosen for the predictive mean matching method. Only patients who did not experience death will be included in the imputation model. Separate imputation models will be used for each treatment group.

The models will contain the following variables (in order of being imputed):

- Baseline eGFR
- Log-serum Albumin at Baseline
- Region (stratification factor)
- Race (stratification factor)
- Sex
- Age
- BMI
- Week 24 eGFR
- Week 36 eGFR
- Week 50 eGFR
- Week 64 eGFR
- Log-serum Albumin at Week 76
- Week 76 eGFR

The imputation will be implemented using the following three standard steps to generate inference from the imputed data. The number of imputations will be set of 100.

1. Imputation step:

- The missing data will be imputed 100 times to generate 100 imputed datasets for the patients who did not experience death.
- Patients who experienced death will be added in each of the datasets to obtain full datasets including all the patients in the analysis population.
- A number of burn-in iterations of 100 and a seed of 5678234 will be used.
- Analysis step: Each of the 100 imputed datasets will be analyzed using ANCOVA model
- 3. **Pooling step:** The results from the 100 imputed datasets will be combined for inference following the methodology developed by Rubin (Rubin 1987).

4.3.1.6 Change in FACIT-F scale from Baseline to Week 76

Change in FACIT-F scale from baseline at Week 76 will be analyzed using ANCOVA model. The response variable in the model will be change in FACIT-F scale from baseline at Week 76. Treatment group, baseline FACIT-F scale and the stratification factors race and region will be included in the model as independent variables. The adjusted difference between the treatment group with 95% CI and p-value will be presented.

The FACIT-F scale for patients who died will be imputed with 0 (composite strategy). All other intercurrent events (specified in Section 4.3) will be handled using treatment policy strategy.

Missing data will be imputed by multiple imputations. Only patients who did not experience death will be included in the imputation model. Multiple imputation methods will be the same as described in Section 4.3.1.5.

The multiple imputation models will contain the following variables (in order of being imputed):

- Baseline FACIT-F score
- Region (stratification factor)

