The C3 values for patients who died will be imputed with LLOQ/2 where LLOQ being the lower limit of quantification. The LLOQ at the central lab is set for C3 at 0.100 g/L. All other intercurrent events (specified in Section 4.3) will be handled using treatment policy strategy.

Missing data will be imputed by multiple imputations using the same methods described in Section 4.3.1.5.

The multiple imputation models will contain the following variables (in order of being imputed):

- Baseline C3
- Region (stratification factor)
- Race (stratification factor)
- Sex
- Age
- Week 4 C3
- Week 12 C3
- Week 24 C3
- Week 50 C3
- Week 76 C3

Inclusion of Week 76 value in the model has minimal impact on the Week 50 imputation. The Week 76 C3 has been added in the imputation model to facilitate the imputation and analysis of C3 at Week 76 which is an exploratory endpoint. Also, to facilitate the analysis of C3 at other visit, patients who experienced death will be included in the imputation model, but imputed values after death will be replaced by the LLOQ/2.

4.3.2.3 Change in SLEDAI-2K from Baseline to Week 76

Change in SLEDAI-2K score from baseline at Week 76 will be analyzed using the same methods as described in Section 4.3.1.5 and Section 4.3.1.

The SLEDAI-2K for patients who died will be imputed with 105 which is the maximum possible SLEDAI-2K value. All other intercurrent events (specified in Section 4.3) will be handled using treatment policy strategy.

The multiple imputation models will contain the following variables (in order of being imputed):

- Baseline SLEDAI-2K
- Region (stratification factor)
- Race (stratification factor)

- Sex
- Age
- Week 24 SLEDAI-2K
- Week 50 SLEDAI-2K
- Week 76 SLEDAI-2K

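### Scoring each death as SLEDAI-2K 105 in a comparison of means lets one or two deaths per arm dominate the Week 76 SLEDAI-2K result

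*SAP*

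**What the plan says.** SAP Section 4.3 handles death before the assessment by a composite strategy for every continuous secondary endpoint: one fixed value, set in advance, replaces data after death. The summary measure is a difference in adjusted means. The other intercurrent events follow treatment policy.

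The fixed values for the three endpoints considered here are:

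- SLEDAI-2K (Section 4.3.2.3, supportive): "The SLEDAI-2K for patients who died will be imputed with 105 which is the maximum possible SLEDAI-2K value".
- eGFR (Section 4.3.1.5, key secondary): "The eGFR values for patients who died will be imputed with 0 (composite strategy)".
- FACIT-F (Section 4.3.1.6, key secondary): "The FACIT-F scale for patients who died will be imputed with 0 (composite strategy)".

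All three are analysed by ANCOVA in each of 100 imputed datasets and pooled by Rubin's rules; the SLEDAI-2K section refers back to the eGFR section for its method. Change in eGFR is the third key secondary endpoint in the testing order of SAP Section 2.1.1, and FACIT-F is the last. SLEDAI-2K is not in that order.

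The SAP specifies no rank-based, robust or other sensitivity analysis for a continuous endpoint. Its tipping-point analysis (Section 4.2.4.2.2) concerns CRR only. Protocol Section 6.3.2.1 says that sensitivity analyses may extend to key secondary endpoints, which would not include SLEDAI-2K.

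**The concern.** ANCOVA compares means and uses one residual variance. A handful of values far outside the survivors' range inflates that variance, and the standard error with it, whether or not the drug works in survivors. If deaths are split evenly, a real difference in disease activity can be hidden. If they are not, the estimate in score points mainly reports the difference in deaths.

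At stake for SLEDAI-2K is an interpretable result on overall lupus activity. The same mechanism acts on eGFR and FACIT-F, and there a failed eGFR test would stop the endpoints behind it, so its size has to be checked separately.

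**Working it through.** **1. The plan's own figure.** The only power statement concerns CRR. Protocol Section 6.1 has "a total of 252 patients randomized to obinutuzumab and placebo groups in a 1:1 ratio" and says this "will yield approximately 90% power to compare the combined obinutuzumab treatment group with the placebo group". With 30% vs 50%, 126 per arm and two-sided 0.05, the pooled-variance formula gives (0.20·√126 − 1.96·√(2·0.4·0.6)) / √(0.3·0.7 + 0.5·0.5) = (2.245 − 1.358)/0.678 = 1.31, or 90.5% power. The stated figure is reproduced. No power, SD, effect or expected death count is given for any continuous endpoint, so everything below rests on assumptions shown as ranges.

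**2. How far 105 lies from survivors.** The item weights in Protocol Appendix 9 are eight 8s, six 4s, seven 2s and three 1s: 64 + 24 + 14 + 3 = 105 over 24 items. A death is therefore scored as if every item were present. With an assumed survivor mean of about 6 at Week 76 (baseline 12), the gap is 105 − 6 = 99 points. One death moves its arm's mean by 99/126 = 0.79 points.

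**3. Variance and power, equal expected deaths per arm.** Let q = deaths/126. Then SD_mix² = (1−q)·SD² + q(1−q)·99². The survivor effect d is set to give 90% power with no deaths: d = 3.242·SD·√(2/126). Power is Φ((1−q)·d / (SD_mix·√(2/126)) − 1.96).

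For SD 6 and two deaths per arm: q = 0.0159, SD_mix² = 35.4 + 153.1 = 188.5, SD_mix = 13.7 and d = 2.45. Power is Φ(2.41/1.73 − 1.96) = 29%.

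| Survivor SD | Deaths per arm | SD with deaths | Variance due to deaths | Power |
|---|---|---|---|---|
| 4 | 1 | 9.6 | 77.2/93.0 = 83% | 27% |
| 6 | 1 | 10.6 | 77.2/112.9 = 68% | 44% |
| 8 | 1 | 11.9 | 77.2/140.7 = 55% | 58% |
| 4 | 2 | 13.0 | 91% | 16% |
| 6 | 2 | 13.7 | 81% | 29% |
| 8 | 2 | 14.7 | 71% | 41% |

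**4. Simulated ANCOVA against worst-rank ANCOVA.** The model is baseline-adjusted with 126 per arm; strata and multiple imputation are left out. With no deaths the residual SD is 4.3 and the mean difference about 1.8 points.

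| Deaths, obinutuzumab / placebo | Planned ANCOVA | Rank ANCOVA |
|---|---|---|
| 0 / 0 | 90.8% | 88.7% |
| 1 / 1 | 10.2% | 84.5% |
| 2 / 2 | 0.3% | 86.0% |
| 4 / 4 | 0.0% | 81.2% |
| 2% / 2%, counts random | 19.6% | 83.1% |

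Power is lower than in step 3 when counts are fixed and equal: the deaths then add nothing to the estimated difference but still inflate its standard error. A second simulation with survivor SDs of 5 to 7 and fixed counts starts near 85%. It falls to 9-24% with one death per arm and 0-3% with two, against 79-83% for rank ANCOVA.

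**5. Unequal deaths.** The only death rates in the documents are those of the Phase II study to Week 76 (Protocol Section 1.3): 2% on obinutuzumab, 7% on placebo. With no effect in survivors the expected SLEDAI-2K difference is (0.02 − 0.07)·99 = −4.95 points; the simulated mean is −4.93. It is significant in obinutuzumab's favour in 48% of trials (rank ANCOVA 12%).

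**6. eGFR and FACIT-F.** The same formula from a 90% start, two deaths per arm:

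| Endpoint (assumed gap) | Survivor SDs | Variance due to deaths | Power |
|---|---|---|---|
| eGFR (100) | 15 / 20 / 25 | 41 / 28 / 20% | 69 / 78 / 82% |
| FACIT-F (39) | 8 / 10 / 12 | 27 / 19 / 14% | 78 / 82 / 85% |

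The loss is 90 − 85 = 5 to 90 − 69 = 21 points. At 2% vs 7% deaths, simulated power rises instead: eGFR from 89% to 95%, FACIT-F from 87% to 94%. SLEDAI-2K falls from 91% to 75%.

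**The case against.** The strongest reply is that this is a declared estimand, not a mistake. The SAP commits to one value fixed in advance for death and to a difference in means, and 105 is the top of the range given in Protocol Section 4.5.7.2. If more patients die on obinutuzumab, losing power is what an analysis that counts death as failure should do. A rank test does not test the declared summary measure, and a survivor-only mean conditions on something that happens after randomisation. Deaths are also reported elsewhere and form part of a key secondary endpoint. All of this stands. It justifies keeping death as the worst outcome and labelling any survivor mean as descriptive. It does not answer the collapse of power when deaths are balanced.

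Three stronger readings are tempting, and the documents do not support them:

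- **That all three endpoints are swamped.** For eGFR and FACIT-F, two deaths per arm supply a minority of the variance, and 0 is the natural floor of the 0-52 FACIT-F scale.
- **That the alpha-controlled sequence is badly weakened.** The collapse belongs to SLEDAI-2K, which gates nothing. eGFR does gate later endpoints, but its loss is moderate and turns into a gain at the only death rates in the documents.
- **That the health authority's feedback left fixed extreme values open, or ruled them out.** The SAP's amendment rationale says only that the intercurrent-event strategy changed in response to feedback. The feedback itself is not shown.

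**Conclusion.** The point holds for SLEDAI-2K. With deaths balanced, one or two per arm supply 55% to 91% of the variance, and power falls from about 85-90% to between roughly 0% and 60%. With deaths unbalanced, the estimate in score points is largely a count of deaths. The figures rest on an assumed gap of about 99 points, survivor SDs of 4 to 8 and chosen effects. They are ranges, not trial figures, but the direction is the same throughout because the gap is so much larger than any plausible SD.

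For eGFR and FACIT-F the effect is moderate: about 5 to 21 points at two balanced deaths per arm, with power rising if deaths fall mainly on placebo. Whether to replace a declared mean difference on alpha-controlled endpoints is a trade-off on which statisticians may reasonably differ, so it need not change there. This is a worthwhile, low-cost improvement to a supportive analysis, not a correction of an internal error.

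**What to change.** In SAP Section 4.3.2.3, keep death as the worst outcome. Base the SLEDAI-2K p-value on rank ANCOVA with deaths at the worst rank, adjusted for baseline, region and race, in each imputed dataset and then pooled. Beside it, report the number of deaths per arm and the mean difference in survivors, labelled as descriptive.

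In Sections 4.3.1.5 and 4.3.1.6, leave the declared ANCOVA as the primary analysis for eGFR and FACIT-F. Add worst-rank ANCOVA as a prespecified sensitivity analysis, with deaths per arm shown next to each estimate.

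The cost is SAP wording and programming; no data collection and no alpha allocation changes. The SLEDAI-2K test would no longer correspond to a raw mean difference, so the estimand text for that endpoint needs to say so. About 1 to 3 points of power are lost if nobody dies.

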4.3.2.4 Time to Onset of CRR Over the Course of 76 Weeks

Time to onset of CRR is defined as the time from randomization to the achievement of CRR as defined in Section 4.2.1 for the first time. Based on the schedule of activities, 24-hour UPCR was measured at baseline, Week 24, 50, and 76; Serum creatinine was measured at baseline, Week 2, 4, 12, 24, 26, 36, 50, 52, 64, and 76, through the 76 weeks of treatment visit. The time to onset of CRR over the course of 76 weeks will be either on Week 24, 50, or 76, depending on the timing when CRR is achieved.

Data will be censored as follows:

- Patients who experience the intercurrent events of rescue therapy, treatment failure, death or early study withdrawal before achieving CRR will be censored at Week 76
- Patients completing the 76-week treatment period who do not experience CRR will be censored at Week 76

Time to CRR will be summarized using Kaplan-Meier curves. A stratified log-rank test will be used to compare the treatment groups (combined obinutuzumab vs. placebo) over the 76 weeks treatment period, adjusting for race and region. Median time to event (when estimable), and their 95% CIs, and a p-value from the log-rank test will be presented. The hazard ratio and its 95% CI will be estimated using a Cox regression model stratified by stratification factors. In fitting the Cox model, ties will be handled with the approximate likelihood method of Efron (1977).

Estimand attributes:

- Population: Patients with active or active/chronic ISN/RPS 2003 Class III or IV proliferative LN
- Endpoint (variable): Time to CRR
- Treatments:
 - Experimental: Obinutuzumab 1000 mg IV infusion at Day 1 and Weeks 2, 24,
 26, and either Weeks 50 and 52 or Week 52 only
 - Control: Placebo
- Intercurrent events: Rescue therapy, treatment failure, study treatment discontinuation, death, or early study withdrawal.

Patients who experience rescue therapy, treatment failure, death, or early study withdrawal before achieving CRR will be censored at Week 76

Study treatment discontinuation will be handled using the treatment policy strategy. Patients who discontinued study treatment will be followed for CRR.

Summary measure: Log rank test and hazard ratio

Intercurrent events are described in Section 4.2.1.1 in details.

4.3.2.5 Proportion of Patients who Achieve CRR with Serum Creatinine Criteria at Week 76

The proportion of patients who achieve CRR with serum creatinine criteria at Week 76 will be analyzed using a CMH test with region and race as stratification factors. CRR with serum creatinine criteria is defined as achievement of all of the following:

- UPCR < 0.5
- Serum creatinine ≤ULN (as determined by the central laboratory)
- Serum creatinine not increased from baseline by >25%
- No occurrence of the following intercurrent events:
 - Rescue therapy, treatment failure, death or early study withdrawal

Intercurrent events are described in Section 4.2.1.1.

Missing data: Data obtained from the central laboratory only will be used. Missing UPCR and serum creatinine data will be imputed by multiple imputations using the model specified in Section 4.2.2 replacing eGFR by serum creatinine in the model. The analysis will follow the same methods described in Section 4.2.2.

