Appendix 5 Renal and Extrarenal Flares: Definitions and Corticosteroid Dosing

RENAL FLARE DEFINITION

Retreatment with higher doses of corticosteroids is permitted for treatment of renal flares if judged necessary by the investigator. Renal flare criteria require at least one of the following to be present (adapted from Rovin et al. 2005):

- Confirmed, clinically-significant increase in urinary protein-to-creatinine ratio (e.g., an increase of ≥50% to a value > 3 that is confirmed with a repeated measurement)
- Confirmed, clinically significant decrease in estimated glomerular filtration rate (eGFR) (e.g., a decrease of ≥30% in eGFR from the previous assessment to a value <60 that is confirmed with a repeated measurement)

EXTRARENAL FLARE DEFINITION

Treatment with higher doses of corticosteroids is permitted for treatment of extrarenal flares if judged necessary by the investigator. An extrarenal flare is defined as a measurable increase in disease activity in one or more nonrenal organ systems involving new or worse clinical signs and symptoms that is clinically significant and prompts consideration of a change or increase in treatment (adapted from Ruperto et al. 2010).

Worsening of systemic lupus erythematosus (SLE) serologies (e.g., C3/C4, anti-dsDNA), or the presence of nonspecific symptoms for which an alternative etiology is likely (e.g., fever), do not, in isolation, constitute extrarenal flares.

SLE disease worsening and flares must be captured in the electronic data capture through the Systemic Lupus Erythematosus Disease Activity Index 2000 score electronic Case Report Form (see Section 4.5.7.2).

CORTICOSTEROID DOSING FOR RENAL AND EXTRARENAL FLARES

In the event of a renal or extrarenal flare, patients may receive prednisone up to 0.5 mg/kg (maximum 60 mg/day) for up to 2 weeks. Prednisone will then be tapered expeditiously to achieve ≤ 10 mg/day by 6 weeks after the initial corticosteroid increase (see Table 1). Subsequently, prednisone will be tapered back to the protocol-mandated dose (see Section 4.3.2.1). IV corticosteroids in equivalent doses may be used temporarily if gastrointestinal involvement temporarily precludes oral corticosteroid use.

Use of pulse steroids or sustained, high-dose oral corticosteroids from Week 64 onward is considered corticosteroid rescue, will result in nonresponse for subsequent efficacy assessments, and should be avoided (see Section 4.4.4.1.1).

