4.2.1.1 Intercurrent Events

The intercurrent events include rescue therapy, treatment failure, study treatment discontinuation, death and early study withdrawal.

Rescue therapy: In some cases of worsening or severely active disease, the investigator may conclude that the patient has failed the randomized treatment regimen and requires rescue therapy.

Two categories of rescue therapies will be considered for the study:

Rescue therapy excluding corticosteroids

Rescue therapies in this category include the following:

Cyclophosphamide

- Anti-CD20 antibodies, including rituximab, ocrelizumab, ofatumumab, and obinutuzumab (if given outside the study protocol)
- Calcineurin inhibitors including ciclosporin, tacrolimus, and voclosporin
- Other investigational, biologic, or targeted therapies used for the treatment of SLE or LN

Patients who receive these rescue therapies will discontinue obinutuzumab or placebo infusions. These patients will continue to be followed according to the study schedule of activities through Week 76 and for at least 12 months from the last dose of obinutuzumab or placebo.

Corticosteroid only rescue

Patients who receive high doses of corticosteroids shortly before the primary endpoint at Week 76 will be considered to have received rescue therapy. Administration of any of the following from Week 64 onward will be considered rescue:

- Methylprednisolone ≥100 mg IV or equivalent
- Prednisone ≥20 mg/day or equivalent (mean dose) over any 2-week period

Any IV or IM corticosteroids will be converted to Methylprednisolone equivalent to evaluate the Methylprednisolone \geq 100 mg IV or equivalent criteria. As for evaluating the prednisone \geq 20 mg/day or equivalent criteria, oral, IV, and IM corticosteroids will be converted to prednisone equivalent dose.

Methylprednisolone pre-medication given prior to obinutuzumab/placebo infusion as per protocol will be exempted from corticosteroid rescue criteria.

Patients who receive corticosteroid rescue will be treated as non-responders. Patients who receive rescue with corticosteroids alone are not required to discontinue obinutuzumab or placebo infusions.

This same rule related to corticosteroid rescue received within 12 weeks prior to endpoint evaluation will also be applied to other secondary and exploratory renal response endpoints (where applicable), including CRR, PRR, ORR, and proteinuric response at Weeks 24, 50, 76, and post Week 76 timepoints.

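### Time to onset of CRR: SAP 4.3.2.4 censors after rescue without a time limit, while SAP 4.2.1.1 ties steroid-only rescue to one evaluation, so read literally a Week 76 primary responder can count as never reaching CRR

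*SAP*

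**What the plan says.** SAP 4.3.2.4 defines the endpoint as time from randomisation to the first CRR. The timing is discrete: "The time to onset of CRR over the course of 76 weeks will be either on Week 24, 50, or 76". The censoring rule is set at patient level: "Patients who experience the intercurrent events of rescue therapy, treatment failure, death or early study withdrawal before achieving CRR will be censored at Week 76". The estimand in the same section repeats it. For what counts as rescue the section gives only a cross-reference: "Intercurrent events are described in Section 4.2.1.1 in details".

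SAP 4.2.1.1 divides rescue therapy in two. Non-steroid rescue (cyclophosphamide, anti-CD20 antibodies, calcineurin inhibitors and other targeted agents) is also treatment failure, which means non-response in all later efficacy analyses. Corticosteroid-only rescue depends on timing. For the primary endpoint: "Administration of any of the following from Week 64 onward will be considered rescue". One of the two triggers is "Prednisone ≥20 mg/day or equivalent (mean dose) over any 2-week period"; the other is methylprednisolone of at least 100 mg IV. The rule is then extended: "This same rule related to corticosteroid rescue received within 12 weeks prior to endpoint evaluation will also be applied". That extension reaches the remaining endpoints based on renal response, subject to a qualifier about applicability, and CRR at Weeks 24, 50 and 76 is among those named.

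Protocol Appendix 5 permits steroid courses for flares that can reach the threshold: "patients may receive prednisone up to 0.5 mg/kg (maximum 60 mg/day) for up to 2 weeks". Under protocol 4.4.4.1.1, a patient with steroid-only rescue need not stop infusions.

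**The concern.** The two sections treat the same fact on different scales. In 4.2.1.1 a steroid course counts against one evaluation. In 4.3.2.4 rescue before first CRR removes the patient from any later event. Because Week 76 is the last possible event time, a patient censored there stays in the risk set at Weeks 24, 50 and 76 and never contributes an event, which is the same as no CRR.

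Two planned analyses of CRR could therefore disagree about the same patient on the same data. The time-to-event analysis yields a hazard ratio, a stratified log-rank p-value and Kaplan-Meier curves, and the choice between readings would be left to the programmer.

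**Working it through.** **1. The plan's own figure.** The SAP gives no power for time to CRR. It gives about 90% for the primary comparison (SAP 2.2: 126 per group, 30% vs 50%, two-sided 0.05). With pooled variance under the null, power = Φ{[0.20·√126 − 1.96·√(2·0.4·0.6)] / √(0.21 + 0.25)} = Φ{(2.245 − 1.358)/0.678} = Φ(1.308) = 0.905. The stated figure is reproduced.

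**2. When the rules can conflict.** The 12-week look-backs are Weeks 12-24, 38-50 and 64-76. Before Week 64, 12 + 12 = 24 of 64 weeks are flagged. The scheduled prednisone dose is 7.5 mg/day from Week 12 and 5 mg/day from Week 24 (protocol 4.3.2.1, Table 2), so only an added course can trigger the rule.

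**3. One patient traced.** No CRR at Week 24; a steroid-only course averaging at least 20 mg/day for two weeks from Week 40; UPCR below 0.5 and eGFR at least 85% of baseline at Week 76; no other intercurrent event.

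| Analysis | Is the course rescue? | Result |
|---|---|---|
| CRR at Week 50 (exploratory) | Yes, within Weeks 38-50 | Non-responder at Week 50 |
| CRR at Week 76 (primary) | No, before Week 64 | Responder |
| Time to CRR, 4.3.2.4 read literally | Yes, before first CRR | Censored at Week 76, no event |

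With cyclophosphamide in place of the steroid course, the patient is a treatment failure and a non-responder in both the primary and the time-to-event analysis, so there is no conflict.

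**4. Size, by illustration.** Inputs from the SAP: 126 per arm and CRR rates of 50% and 30%, taken here as the share with a first CRR by Week 76. This gives 126 × 0.50 = 63.0 and 126 × 0.30 = 37.8 expected events. Assumed, because the documents give no figures:
- First CRR is split equally over Weeks 24, 50 and 76.
- A share f of first-at-Week-76 responders, and f/2 of first-at-Week-50 responders, had an earlier flagged course.

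Events kept in an arm with total T are T/3 + (T/3)(1 − f/2) + (T/3)(1 − f). For T = 63 and f = 0.2 this is 21 + 18.9 + 16.8 = 56.7.

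The unstratified log-rank over three times uses E = Σ D·n₁/N and V = Σ D·n₁·n₂·(N − D)/[N²(N − 1)], with Z = (O − E)/√V, HR ≈ exp[(O − E)/V] and power ≈ Φ(Z − 1.96). With no reclassification, O = 63.0, E = 48.23 and V = 21.29, so Z = 14.77/4.614 = 3.20, HR = exp(0.694) = 2.00 and power = Φ(1.24) = 0.89.

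| f obinutuzumab / placebo | Events | HR | Power |
|---|---|---|---|
| 0 / 0 (visit-by-visit rule) | 63.0 / 37.8 | 2.00 | 0.89 |
| 10% / 10% | 59.9 / 35.9 | 1.97 | 0.87 |
| 20% / 20% | 56.7 / 34.0 | 1.95 | 0.84 |
| 20% / 40% | 56.7 / 30.2 | 2.20 | 0.93 |
| 20% / 10% | 56.7 / 35.9 | 1.84 | 0.78 |

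If first CRR is split 20/30/50% instead, the HR without reclassification is 2.01. The two unequal scenarios then give 2.28 (20% / 40%) and 1.79 (20% / 10%).

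**The case against.** The strongest reply is that the text can be read without conflict, in either of two ways.

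- **Only the Week 64 definition applies.** The Week 40 course is then not rescue at all. This removes the conflict with the primary but creates another. A patient with a flagged course at Week 45 who meets the laboratory criteria at Week 50 would have onset at Week 50 here, yet be a non-responder in the exploratory Week 50 CRR analysis, where the 12-week rule is explicit.
- **The look-back is applied visit by visit.** The Week 40 course then blocks Week 50 only. This reading agrees with both binary analyses, and the words of 4.2.1.1, including its allowance for applicability, leave room for it. But 4.3.2.4 does not say it, and its censoring sentence, given twice, points the other way.

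The reply does succeed against several stronger readings that a reader might infer:

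- **That every kind of rescue conflicts.** Non-steroid rescue does not, because it is permanent failure in the primary too.
- **That any flare course conflicts.** It must meet the threshold, fall in Weeks 12-24 or 38-50, and precede any CRR.
- **That a course started just before Week 38 escapes.** It need not. In the Appendix 5 table, a 30 mg start at Week 36 is followed by 25 and then 20 mg/day over Weeks 38-40, a mean of (25 + 20)/2 = 22.5, which is still flagged. A look-back edge would also remain under any visit-by-visit rule.
- **That the bias favours obinutuzumab.** This needs more flagged courses on placebo, and the documents give no rates by arm.

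**Conclusion.** The point holds for corticosteroid-only rescue. Followed as written, 4.3.2.4 can score a primary responder as never achieving CRR. This is an inconsistent result from a stated rule, and more than missing detail.

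The size is unknown, since it depends on how often qualifying courses occur in each arm before a later first CRR. On the assumptions above, equal reclassification loses events and power and pulls the hazard ratio slightly toward 1 (2.00 to 1.95 at 20%). Unequal reclassification can move it either way (1.84 to 2.20 with an equal split, 1.79 to 2.28 with a later split). These figures illustrate the mechanism and do not predict the trial's result.

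Time to onset of CRR is a supportive secondary endpoint and is not in the testing sequence of SAP 2.1.1. The primary analysis, its type I error, the sample size of 252 and the 90% power are unaffected. The correction is worth making because it is cheap and removes a choice that could otherwise be made after the data are seen.

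**What to change.** In SAP 4.3.2.4, in both the censoring list and the estimand, limit permanent censoring at Week 76 to non-steroid rescue, treatment failure, death and early study withdrawal before CRR. Add that CRR is evaluated at Weeks 24, 50 and 76 with the 12-week corticosteroid look-back of 4.2.1.1, that corticosteroid-only rescue makes the patient a non-responder only at the evaluation concerned, and that a later first CRR counts as an event. If permanent exclusion is intended instead, state that and give the reason.

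The cost is a short SAP edit and a small change to the derivation. No extra data are needed. This is an analysis rule only and does not alter steroid management in the trial.
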